## 2 Trial Rationale and Objectives

### 2.1 Trial Rationale

The purpose of this trial is to establish the effects of tolvaptan on serum sodium concentration as well as the safety of use of tolvaptan in children and adolescents with euvolemic or hypervolemic hyponatremia secondary to [REDACTED] [REDACTED]. In addition, blood samples will be taken to determine tolvaptan PK specific to a pediatric population, as the absorption, distribution, metabolism, and elimination of drugs in children and adolescents can vary from that of adults. These differences can be due to differences in physiology based on maturity status (eg, GI transit times are faster, the ratio of total body water to body fat is shifting, and the expression of drug metabolizing enzymes change) or based on underlying disease state. Hyponatremia alone does not appear to affect tolvaptan PK; however, tolvaptan exposure is 2-fold greater in adult subjects with CHF compared to healthy adult subjects and clearance appears to decrease about 50% in subjects with moderate to severe hepatic failure (Child-Pugh score > 6). As the primary pharmacodynamic effect of tolvaptan is to produce an increase in urine output (aquaresis), urine output and fluid intake will be determined as PD endpoints.

The proposed population size of 100 subjects is expected to yield 70 subjects who respond to tolvaptan (henceforth termed “responders”), which has adequate power (> 90%) to test for statistical significance in the primary endpoint. Enrollment is expected to take approximately 3 years using approximately 60 sites globally. Additional blood sampling will be included across populations to provide PK information.

Even with a limited size, recruitment for such a trial is expected to be challenging due to the low frequency of AVP-mediated hyponatremia in children. Therefore, the trial will be organized at major pediatric referral centers to access the largest patient population.

It is recognized that the pediatric population is a vulnerable subgroup and there are risks in conducting a clinical trial in the pediatric population. However, given the possible serious and life-threatening consequences of untreated hyponatremia, it is necessary to study hyponatremia treatment in children. Children have different physiology and metabolisms from adults and, therefore, it is not sufficient to study hyponatremia treatment in the adult population to determine the proper course of treatment for hyponatremia in the pediatric population. A clear understanding of exposure-response in adults that can be applied to pediatrics (or from one pediatric group to another) has not yet been established, furthering the need for this trial.

Every effort will be made to anticipate and reduce known risks. This trial was designed to minimize the number of participants and the number of procedures, consistent with good study design. Children will be continuously monitored for signs of distress during this trial. The risk threshold for subjects will be constantly monitored by the investigator. A detailed list and description of the safety monitoring to be conducted during this trial can be found in Section 3.7.4.

### 2.1.1 Dosing Rationale

Enrolled subjects will be dosed based on formulation type, age, weight, and the use of CYP3A4 inhibitors.

In the pivotal hyponatremia trials the starting 15-mg dose was administered to adult subjects weighing 34.0 to 164.7 kg; in terms of mg/kg, the starting dose of tolvaptan ranged from 0.09 to 0.44 mg/kg. The weight cutoffs for use of tolvaptan tablets in this trial were selected to produce mg/kg doses of tolvaptan within the range observed for the adult trials. Table 2.1.1-1 outlines the mg/kg dose ranges for tolvaptan tablet doses and body weights of 10, 20, 50, 70 (standard adult man), and 100 kg.

**Table 2.1.1-1 Starting Tolvaptan Tablet Doses as mg/kg of Body Weight**

Tolvaptan Tablets	Tolvaptan Doses as mg/kg				
	BW of 10 kg	BW of 20 kg	BW of 50 kg	BW of 70 kg	BW of 100 kg
3.75 mg	0.375	0.19	-	-	-
7.5 mg	-	0.375	0.15	-	-
15 mg	-	-	0.30	0.21	0.15

BW = body weight.

Tolvaptan is metabolized by the CYP3A isozyme. At birth, the amount of CYP3A per gram of liver is less than in an adult, but adult levels of CYP3A are reached by 2 years of age. A physiologically-based pharmacokinetic model of adult tolvaptan concentrations was modified to estimate tolvaptan concentrations in subjects from  $\geq 4$  weeks (or  $\geq 44$  weeks of adjusted gestational age) to  $< 2$  years of age and in subjects  $\geq 2$  to  $< 4$  years of age. It was estimated that doses of 0.1 mg/kg and 0.15 mg/kg, respectively, of the suspension would produce peak tolvaptan concentrations similar to those produced by a 15 mg tablet in an adult subject. However, overall exposure for the suspension as determined by AUC would be 33% and 13% lower, respectively, for subjects  $< 2$  years of age and subjects  $\geq 2$  to  $< 4$  years of age when compared to a 15 mg tablet in an adult. It is expected that a 0.15 mg/kg starting dose of tolvaptan suspension would also be suitable for children  $> 4$  years of age, as CYP3A expression would be the same as for children  $\geq 2$  to 4 years of age. Suspension will only be administered to

children who weigh 30 kg or less to limit the amount of sorbitol administered; a 30 kg child titrated to a 0.6 mg/kg dose of tolvaptan suspension would receive 18 mL of tolvaptan suspension, containing approximately 9.6 g of sorbitol.

Tolvaptan is a sensitive CYP3A4 substrate; plasma concentrations increased approximately 4-fold when tolvaptan was administered with the potent CYP3A4 inhibitor ketoconazole. Where appropriate dose reductions are possible, tolvaptan doses may be coadministered with potent or moderate CYP3A4 inhibitors. [Table 3.2.3-1](#) outlines starting dose adjustments when tolvaptan is administered concurrently with potent or moderate CYP3A4 inhibitors.

## **2.2 Trial Objectives**

### **2.2.1 Primary Objective**

The primary objective is to demonstrate that tolvaptan effectively and safely increases and maintains serum sodium concentrations in children and adolescent subjects with euvolemic or hypervolemic hyponatremia.

[figure not shown]
### **2.2.2 Secondary Objectives**

The key secondary objective is to assess the PK of tolvaptan and the effect on fluid balance in children and adolescent subjects with euvolemic or hypervolemic hyponatremia.

## **3 Trial Design**

### **3.1 Type/Design of Trial**

This is an open-label, multicenter, multiple-dose, randomized withdrawal, parallel-group trial of tolvaptan in children and adolescents hospitalized with chronic euvolemic or hypervolemic hyponatremia (serum sodium < 130 mEq/L [mmol/L]) persisting despite initial standard therapy. A schematic of the trial design is provided in [Figure 3.1-1](#).

**PI = Principal investigator.**

### Figure 3.1-1 Trial Design Schematic

### **3.1.1 Trial Phases**

Screening should be performed on Days -2 to -1 to confirm eligibility, followed by the 3 trial phases described in [Section 3.7.1](#).

#### **3.1.1.1 Treatment Phase A**

All subjects will initially receive tolvaptan once daily on Days 1 and 2. If a subject's serum sodium level has not increased by at least 4 mEq/L (mmol/L) by Day 2, an additional day of treatment is required and is referred to as Day 2a. If subjects do not achieve an increase in serum sodium concentration of  $\geq 4$  mEq/L (mmol/L) on Day 2a, they will be defined as nonresponders. If subjects achieve an increase in serum sodium concentration of  $\geq 4$  mEq/L (mmol/L) on Day 2 (or 2a) they will be defined as responders.

#### **3.1.1.2 Treatment Phase B**

On Day 3 responders will be randomized ([Section 3.1.1.2.1](#)) to either the Early Withdrawal group or the Late Withdrawal group. Nonresponders will not be randomized.

For nonresponders from Treatment Phase A, the investigator will determine if the subject is to either:

- Continue treatment with study drug or
- Prescribe treatment per local standard of care for Days 3 and 4.

#### **3.1.1.2.1 Randomization**

Responders will be randomized to either:

- Late Withdrawal group - subjects continue tolvaptan treatment on Days 3 and 4
- Early Withdrawal group - subjects do not receive additional tolvaptan treatment on Days 3 and 4.

Randomization will be stratified by age [REDACTED] [REDACTED], serum sodium response [REDACTED], and underlying hyponatremia etiology [REDACTED].

Subjects randomized to the Early Withdrawal group will be observed to determine whether additional intervention is required to maintain appropriate serum sodium levels. Subjects whose serum sodium declines by  $\geq 4$  mEq/L (mmol/L) or whose overall clinical condition requires further treatment to raise serum sodium levels should be treated per local standard of care. Any intervention intended to raise serum sodium concentration during the first 48 hours of the Early Withdrawal phase (including fluid restriction) will be defined as rescue therapy. Subjects receiving rescue therapy will be considered to

have reached their clinical endpoint, and their data will be censored from that time forward.

### **3.1.1.3 Follow-up Phase C**

All subjects will have an additional serum sodium measurement at 72 ( $\pm$  4) hours post-last dose and 7 (+ 1) days post-last dose. A final safety follow-up telephone contact/visit will be performed 14 (+ 2) days post-last dose.

## **3.2 Trial Treatments**

### **3.2.1 Tablet Formulation**

Tolvaptan tablets will be administered orally once daily, preferably in the morning hours, with a dose proportional amount of water, as follows:

- Doses of  $\geq$  15 mg tolvaptan will be given with 240 mL of water.
- Doses of 7.5 mg tolvaptan will be given with 120 mL of water.
- Doses of 3.75 mg of tolvaptan will be given with 60 mL of water.

The treatment duration will be up to 5 days. Any initiation or titration of tolvaptan must occur in a hospital setting.

The maximum starting doses, by weight, age, and CYP3A inhibitor, for subjects are shown in [Table 3.2.3-1](#) and are within the range previously used in trials involving adult hyponatremic subjects.

The investigator has the option of performing a swallow test and providing coaching on swallowing techniques using placebo tablets if it is unknown if the subject is able to swallow tablets. Placebo tablets will be provided for use in performing this test during screening.

### **3.2.2 Suspension Formulation**

Tolvaptan suspension, 1 mg/mL (0.1% w/v), will be administered orally once daily, preferably in the morning hours. The treatment duration will be up to 5 days. Any initiation or titration of tolvaptan must occur in a hospital setting.

The maximum starting doses for subjects, by weight, age, and CYP3A inhibitor are shown in [Table 3.2.3-1](#).

### **3.2.3 Dosing Guidelines**

Subjects will be administered tolvaptan on a formulation, age- and weight-based scale.

**Table 3.2.3-1** outlines starting tolvaptan doses and adjustments when tolvaptan is administered concurrently with potent or moderate CYP3A inhibitors. Tolvaptan doses will be reduced 75% and 50% if a potent or moderate inhibitor, respectively, is being concurrently administered. As the smallest volume of suspension that can be administered is 0.3 mL (0.3 mg), subjects weighing < 3 kg, < 6 kg and taking a moderate or a potent CYP3A4 inhibitor, or weighing < 12 kg and taking a potent CYP3A4 inhibitor may not be enrolled. Suspension should be administered with the syringes provided.

Table 3.2.3-1 Starting Tolvaptan Doses With or Without Potent or Moderate CYP3A Inhibitors				
Age/Weight	Can subject swallow a tablet?	Starting Dose: No CYP Inhibitor	Starting Dose: Moderate CYP Inhibitor	Starting Dose: Potent CYP Inhibitor
≥ 4 wk (or ≥ 44 wk adjusted gestational age) to < 2 y AND ≥ 3 kg to < 6 kg c	N/A	0.1 mg/kg suspension a,b	Not eligible for treatment	Not eligible for treatment
≥ 4 wk (or ≥ 44 wk adjusted gestational age) to < 2 y AND ≥ 6 to < 12 kg c	N/A	0.1 mg/kg suspension a,b	0.05 mg/kg suspension	Not eligible for treatment
≥ 2 y to ≤ 6 y AND ≤ 30 kg c	N/A	0.15 mg/kg suspension	0.08 mg/kg suspension	0.04 mg/kg suspension
> 6 y AND ≤ 30 kg	No	0.15 mg/kg suspension	0.08 mg/kg suspension	0.04 mg/kg suspension
> 6 y AND 20 to 50 kg	Yes	7.5 mg tablet	3.75 mg tablet	1.90 mL suspension
> 6 y AND > 50 kg	Yes	15 mg tablet	7.5 mg tablet	3.75 mg tablet

a The smallest volume of suspension that may be administered is 0.3 mL (0.3 mg), therefore dose reductions cannot be accommodated for children < 6 kg taking moderate inhibitors and for children < 12 kg taking potent inhibitors.

b Tolvaptan suspension is provided in a concentration of 1 mg/mL.

c Suspension required (pediatric subjects ≤ 6 years of age and ≤ 30 kg body weight).

Titration of tolvaptan doses can occur once daily and will be based on serum sodium levels assessed at > 20 hours following initiation of therapy and each subsequent dose; titration may not occur within 24 (± 4) hours of the previous dose. Up-titration is limited to no more than twice the previous dose.

- Subjects ≥ 4 weeks (or ≥ 44 weeks adjusted gestational age) to < 2 years of age and weighing ≥ 3 kg to < 6 kg will receive 0.1 mg/kg of the suspension on Day 1 with possible up-titration to 0.2 mg/kg and 0.4 mg/kg doses.
- Subjects ≥ 4 weeks (or ≥ 44 weeks adjusted gestational age) to < 2 years of age and weighing ≥ 6 kg to < 12 kg will receive 0.1 mg/kg of the suspension on Day 1 with possible up-titration to 0.2 mg/kg and 0.4 mg/kg doses.

- Subjects  $\geq 2$  to  $\leq 6$  years of age, weighing  $\leq 30$  kg will receive a 0.15 mg/kg dose of the suspension on Day 1 with possible up-titration to 0.3 mg/kg and 0.6 mg/kg doses.
- Subjects  $> 6$  years of age, weighing  $\leq 30$  kg and who cannot safely swallow a tablet, will receive a 0.15 mg/kg dose of the suspension on Day 1 with possible up-titration to 0.3 mg/kg and 0.6 mg/kg doses.
- Subjects  $> 6$  years of age and weighing 20 to 50 kg, inclusive, will receive a 7.5 mg tablet on Day 1 with possible up-titration to 15-mg and 30-mg doses.
- Subjects  $> 6$  years of age and weighing  $> 50$  kg, will receive a 15 mg tablet on Day 1 with possible up-titration to 30-mg and 60-mg doses.

[figure not shown]
Following their initial tolvaptan dose in the trial, subjects will continue dosing according to the titration scheme (see [Section 3.2.4](#)), targeting a final serum sodium concentration between 135 and 140 mEq/L (mmol/L). Titration guidelines are designed to achieve a change in serum sodium concentration of at least 4 to 8 mEq/L (mmol/L)/24 hours but not [REDACTED].

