There is the potential for osmotic diarrhea due to the sorbitol content in the suspension. D-Sorbitol is a hexahydric sugar alcohol that naturally occurs in fruits and animal tissue. The daily per capita consumption of sorbitol as a food ingredient is approximately 200 mg. The compound is about 35-60% as sweet as sugar, and has been the impetus as a substitute for sugar to reduce caloric intake and prophylactic measures against the formation of dental caries. Absorption of sorbitol by humans is limited by its rate of diffusion from the GI tract and by laxation that may occur after ingestion of high doses. Typically, 25-50 g in adults may cause osmotic diarrhea. The corresponding dose in children is thought to be 10 g and higher, but is dependent on body weight and types of foods ingested. Similar findings are also observed with other sugar alcohols, eg, xylitol.

Following a single 15 mg tolvaptan dose of the suspension, containing 8 g of sorbitol, in healthy adults, no diarrhea was reported.

Therefore, in this trial, suspension dosing is limited to subjects who weigh  $\leq$  30 kg; the maximum dose of sorbitol is expected to be approximately 9.6 grams in a 0.6 mg/kg dose for a subject who weighs 30 kg. Subjects will be started on the lowest dose for their weight and titrated to higher doses as appropriate for their clinical condition. Subjects will be in a hospital setting during titration and will be closely monitored for rate of sodium correction and signs of dehydration including diarrhea.

Analyses of the completed 3-year pivotal Trial 156-04-251 (double-blind, placebo-controlled trial to determine long-term safety and efficacy of oral tolvaptan in adult subjects with ADPKD) have revealed new and important safety information. In this trial, a new signal for imbalanced elevations of liver transaminases in ADPKD subjects

receiving tolvaptan compared with placebo was detected and formally adjudicated by an expert panel blinded to treatment.

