### 3.4.2 Inclusion Criteria

Subjects are required to meet the inclusion criteria presented in [Table 3.4.2-1](#).

Table 3.4.2-1 Inclusion Criteria	
1.	Male and female subjects $\geq$ 4 weeks (or $\geq$ 44 weeks adjusted gestational age) to $<$ 18 years old
2.	Subjects hospitalized with euvolemic or hypervolemic hyponatremia resistant to initial standard background therapy (including fluid restriction and excluding a vasopressin antagonist) and who are deemed by the investigator as likely to benefit from a therapy that raises serum sodium levels
3.	Persistent euvolemic or hypervolemic hyponatremia defined as being documented as present for at least 48 hours, evidenced by at least 2 serum sodium assessments $<$ 130 mEq/L (mmol/L) drawn at least 12 hours apart (these values can be documented using historical values previously obtained per standard of care); a third (STAT) serum sodium assessment $<$ 130 mEq/L (mmol/L), which will serve as the baseline value for final trial qualification and clinical management strategy, is to be obtained within 2-4 hours prior to the first dose of tolvaptan
4.	Ability to take oral medication
5.	Ability to maintain adequate fluid intake whether orally or via IV support with adequate monitoring
6.	Ability to comply with all requirements of the trial
7.	Trial-specific written informed consent/assent obtained from a parent/legal guardian or legally acceptable representative, as applicable per age of subject or local laws, prior to the initiation of any protocol-required procedures. In addition, the subject as required by local laws must provide informed assent at Screening and must be able to understand that he or she can withdraw from the trial at any time. All informed consent/assent procedures must be in accordance with the trial center's IRB/IEC and local regulatory requirements
8.	Ability to commit to remain fully abstinent (periodic abstinence [eg, calendar, ovulation, symptothermal, post-ovulation methods] or withdrawal are not acceptable methods of contraception) or practice double-barrier birth control during the trial and for 30 days following the last dose of IMP for sexually active females of childbearing potential

IMP = investigational medicinal product.

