### 3.4.3 Exclusion Criteria

Subjects will be excluded if they meet any of the exclusion criteria in [Table 3.4.3-1](#).

Table 3.4.3-1 Exclusion Criteria	
1.	Has evidence of hypovolemia or intravascular volume depletion (eg, hypotension, clinical evidence of volume depletion, response to saline challenge); if the subject has systolic blood pressure or heart rate outside of the normal range for that age volume status should be specifically clinically assessed to rule out volume depletion.
2.	Has serum sodium $<$ 120 mEq/L (mmol/L), with or without associated neurologic impairment (ie, symptoms such as apathy, confusion, or seizures)
3.	Current use or expected use during the trial of a potent CYP3A4 inhibitor in subjects weighing $<$ 12 kg or a moderate CYP3A4 inhibitor in subjects weighing $<$ 6 kg
4.	Lacks free access to water (inability to respond to thirst) or without ICU-level fluid monitoring and management
5.	Has a history or current diagnosis of nephrotic syndrome
6.	Has transient hyponatremia likely to resolve (eg, head trauma or post-operative state)
7.	Has hyperkalemia defined as serum potassium above the ULN for the appropriate pediatric age range

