22.	Has any medical condition that, in the opinion of the investigator, could interfere with evaluation of the trial objectives or safety of the subjects.
23.	Is deemed unsuitable for trial participation in the opinion of the investigator
24.	Participation in another investigational drug trial within the past 30 days, without prior approval from the sponsor medical monitor
25.	Subjects who weigh < 3 kg
26.	Unable to swallow tablets if the suspension formulation is unavailable
27.	Subjects who require the suspension formulation and have Hereditary Fructose Intolerance

eGFR = estimated glomerular filtration rate; ICU = intensive care unit.

Use of the suspension formulation is at the discretion of the local regulatory authorities and IRB/IECs.

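### The starting-dose table and dose lists leave three eligible groups of children without a dose, conflict with each other for a fourth, and assign suspension above the protocol's own 30-kg limit.

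*Protocol*

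**What the plan says.** Protocol 3.2.1 and 3.2.2 send sites to Table 3.2.3-1, "Starting Tolvaptan Doses With or Without Potent or Moderate CYP3A Inhibitors", for starting doses of both formulations. The table has six rows defined by age, weight and swallowing ability, each with columns for no inhibitor, a moderate inhibitor and a potent inhibitor. The highest weight band under 2 years is "to < 2 y AND ≥ 6 to < 12 kg". The list in 3.2.3 and the synopsis give the no-inhibitor doses in the same age and weight bands.

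Eligibility is wider than the table:
- Table 3.4.2-1 admits ages from 4 weeks to under 18 years.
- The only general weight criterion in Table 3.4.3-1 is criterion 25, "Subjects who weigh < 3 kg". There is no upper weight limit at any age.
- Criterion 3, "Current use or expected use during the trial of a potent CYP3A4 inhibitor in subjects weighing" under 12 kg, also covers moderate inhibitors under 6 kg.
- Criterion 26 excludes children "Unable to swallow tablets if the suspension formulation is unavailable".

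On suspension, section 1.3 says that "in this trial, suspension dosing is limited to subjects who weigh" 30 kg or less. Section 2.1.1 restricts it to "children who weigh 30 kg or less to limit the amount of sorbitol administered". Neither states an exception.

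**The concern.** A dosing table should cover everyone whom the eligibility criteria let in. Where it does not, a site that finds a child otherwise eligible has no protocol dose to give. Where the table and the lists differ, or the table and the suspension limit differ, the site has two instructions and no rule for choosing between them.

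The starting dose is a core safety instruction here: section 5.3.1.1 names overly rapid sodium correction as a hazard of treatment. The first two groups without a dose also lie under 10 years, the band that must supply at least 50% of subjects under section 3.3.

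**Working it through.** **Coverage.** Inputs are the six rows of Table 3.2.3-1, the lists in 3.2.3 and the synopsis, the age range in Table 3.4.2-1, and exclusion criteria 3, 25 and 26. Eligible combinations of age, weight (3 to 100 kg in 0.5-kg steps), swallowing ability and inhibitor use were set against the table rows. No combination matched more than one row. The combinations that matched none form four blocks:

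| Eligible group | Table 3.2.3-1 | Lists (3.2.3, synopsis) |
|---|---|---|
| Under 2 y, 12 kg or more | no row; bands stop below 12 kg | no entry |
| 2 to 6 y, over 30 kg | no row; band stops at 30 kg | no entry |
| Over 6 y, under 20 kg, can swallow | no row; tablet rows start at 20 kg | no entry |
| Over 6 y, over 30 kg, cannot swallow | no row; the non-swallower row stops at 30 kg | tablet, with no swallowing condition |

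In the table, each block is empty in all three inhibitor columns. For the third, the eligible weights run from 3 kg with no inhibitor, from 6 kg with a moderate one and from 12 kg with a potent one, in each case to under 20 kg.

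The first three blocks are absent from table and lists alike. The fourth is a conflict: the list entries for 20 to 50 kg and for over 50 kg do not mention swallowing, while the corresponding table rows require it.

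**First group and the inhibitor floor.** The smallest measurable suspension dose is 0.3 mg, the dose under 2 years is 0.1 mg/kg, and a potent inhibitor cuts the dose by 75%. So 0.3 / (0.1 × 0.25) = 12 kg, which reproduces the weight floor in criterion 3. A child under 2 years on a potent inhibitor therefore passes that criterion at exactly the weight where the table's rows for that age end.

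**Third group and Table 2.1.1-1.** That table lists a 3.75 mg starting tablet at 10 kg and 20 kg (0.375 and 0.19 mg/kg). No cell in the no-inhibitor column of Table 3.2.3-1 uses this tablet.

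**Suspension above 30 kg.** One cell does this: over 6 years, 20 to 50 kg, able to swallow, potent inhibitor, 1.90 mL suspension. It covers over 30 to 50 kg.

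The plan's own sorbitol figure (section 2.1.1) comes first:
- Volume at 30 kg and 0.6 mg/kg, at 1 mg/mL: 30 × 0.6 / 1 = 18 mL.
- Sorbitol concentration from section 1.3: 8 g in a 15 mg dose, or 15 mL, so 8 / 15 = 0.533 g/mL.
- Sorbitol: 18 × 0.533 = 9.6 g. This matches the protocol.

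The cell in question:
- Starting dose: 1.90 × 0.533 = 1.01 g.
- If doubled twice (an assumption, taking each up-titration at its maximum of twice the previous dose): 7.6 × 0.533 = 4.05 g.

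Both are below 9.6 g.

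**The case against.** The strongest reply has four parts.

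*Other provisions catch these children.* Criterion 23 lets the investigator judge a child unsuitable, so not enrolling is an alternative to improvising a dose. That stands as a practical outlet, but it supplies neither a dose nor a stated exclusion. Criterion 26 might be stretched to non-swallowers over 30 kg, since suspension is barred to them by weight. It reads more naturally as unavailability of the formulation at the site, so it leaves ambiguity rather than cover.

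*There are not four missing doses.* A reader of the table alone might infer four. This part of the reply is right: the lists do reach the over-30-kg non-swallower, with a tablet. The defect there is a conflict between table and lists.

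*The suspension cell does no harm to the sorbitol safeguard.* A reader might infer a breach of it. The documents do not support that: the load is about 1.0 g at the start and about 4.1 g after two doublings. Only the written limit is contradicted.

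*The consequences for the data are small.* A reader might infer that off-protocol doses would distort the pharmacokinetic or Phase A response results. Nothing in the documents shows how many children fall in these groups, and SAP 5.1 records extremely low enrollment and early termination, with efficacy reduced to summary statistics. That inference is not supported. Early termination limits the forward effect but does not make the text consistent.

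**Conclusion.** The point holds as an internal inconsistency in a safety-critical table:
- three eligible groups with no starting dose in the table or the lists;
- one group, over 6 years and over 30 kg and unable to swallow, on which table and lists conflict;
- one cell that contradicts the 30-kg suspension limit as written, for children over 30 to 50 kg;
- one tablet strength in Table 2.1.1-1 that the no-inhibitor column of Table 3.2.3-1 does not use.

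This rests on reading the age, weight and swallowing limits literally and on the exclusion criteria being complete as printed. The documents give no weight distribution, so the number of children affected cannot be derived. Some groups, such as 2 to 6 years and over 30 kg, may be rare. No claim is made that a subject was misdosed or that any result is biased.

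**What to change.** Reconcile five places: Table 3.2.3-1; the dose lists in 3.2.3 and the synopsis; Table 2.1.1-1; the 30-kg suspension statements in 1.3 and 2.1.1; and the eligibility criteria in Tables 3.4.2-1 and 3.4.3-1. Afterwards, every eligible combination of age, weight, swallowing ability and inhibitor use should have one consistent entry or an explicit exclusion, and the potent-inhibitor cell for 20 to 50 kg should agree with the stated suspension limit. Which doses, formulations and limits apply is for the sponsor to determine.

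The cost is protocol wording. The sample size and the planned analyses need no change.
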